2. V1 of this extension trial should be preferably performed during the EOS of the preceding BI 655130 parent trial. When the visits are performed on the same day duplicate procedures across studies are performed once during the EOS/V1. If these visits are not performed on the same day then all V1 procedures need to be performed at that visit. The only exception is Infection Testing which does not have to be repeated if performed at EOS of the parent trial and there is a <12 week gap from EOS of parent trial to V1 of this trial. Refer also to [Section 6.2.1](#)
3. After the individual patient's end of the trial the investigator should report only any cancers of new histology and exacerbations of existing cancer, study treatment related SAEs and study treatment related AESIs of which the investigator may become aware of and only via the BI SAE form. Refer to [Section 5.2.6.2.1](#).
4. All patients who receive at least one dose in the trial, including those who discontinue treatment prematurely, should complete the EOT visit as soon as possible and complete the EOS visit 16 weeks after the date of last trial drug administration.
5. Where possible, electrocardiogram (ECG) measurements should precede blood sampling and drug administration. Refer to [Section 5.2.4](#)
6. Body Surface Area (BSA) will be calculated from Part A of the SCORAD. All assessments must be done prior to trial drug administration. The questionnaires completed by patients should be done first before the investigator assessments. Refer to [Section 6.2](#)
7. Only applicable for women of childbearing potential. Urine pregnancy tests will be performed at all visits indicated in the [Flow Chart](#). Urine pregnancy testing should be done prior to administration of study drug. Study drug should only be administered in case of a negative test result. In case of a positive urine pregnancy test, a serum pregnancy test will be performed at the central laboratory.
8. Complete Physical Examination (PE) includes general appearance as well as evaluation of all organ systems.
9. Targeted physical examination includes evaluation of organ systems associated with AE(s) symptoms or laboratory abnormalities.
10. Vital signs will be assessed pre dose as well as within 1 hour post dose.
11. Safety laboratory tests include clinical chemistry, haematology, coagulation, and urinalysis, and will be performed centrally. Where possible, safety laboratory tests are to be drawn prior to dosing.

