6.2.3 End of Treatment and Trial Completion

For all treated patients termination of trial medication and trial completion must be recorded on the corresponding eCRF.

For the comprehensive list of the trial procedures required at the EOT and the EOS visits please refer to [Flow Chart](#).

The EOS visit must be performed 16 weeks after the date of last drug administration.

Early Treatment and Trial Discontinuation:

If trial treatment is discontinued prematurely prior to the planned [Flow Chart](#) EOT visit, every effort should be made to have the patient return and undergo the procedures for the EOT visit as well as the EOS visit 16 weeks after the last study drug administration as outlined in the [Flow Chart](#).

Patients who are unable to physically return to the study site for the EOT and EOS visits should be contacted by the site by phone to collect information pertaining to adverse events and changes to concomitant therapy.

Trial Completion:

Trial completion is defined as a patient having reached the EOS visit within the specified window per protocol.

Treatment Completion:

Treatment completion is defined as a patient completing Visit 52 which is the EOT visit after receiving approximately 4 years of treatment

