5. ENDPOINT(S)

For all endpoints and unless explicitly specified otherwise, Week numbers refer to specific Visit numbers using extended time windows as defined in [Table 6.7: 1](#).

For all endpoints and unless explicitly specified otherwise, End-of-Study visit refers to V53 (Week 220), using extended time windows as defined in [Table 6.7: 1](#).

For handling of missing data and corresponding sensitivity analyses, see [Section 6.6](#).

Definition of baseline is provided in [Section 6.7](#).

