6.7 BASELINE, TIME WINDOWS AND CALCULATED VISITS

Measurements reported with date and time and taken prior to start of administration of trial treatment will be considered pre-treatment values. Measurements reported with a date only (and no time) and taken on the day of first administration of trial treatment will also be considered pre-treatment values. These pre-treatment values will be assigned to visits according to the nominal visit number as recorded on the eCRF or as provided by the laboratory. For definitions used in Safety analyses, refer to [Section 7.8](#).

There will be two different baseline definitions used in the analyses:

1. Baseline for this extension trial – defined as the last measurement recorded before the first trial medication administration in this study.

2. Baseline for the parent trial (1638-0032) – defined as the measurement recorded at randomisation visit (Visit 2) of the parent trial. If the data at Visit 2 is missing, then the data from Visit 1 of the parent trial will be considered baseline.

Two separate analyses will be conducted, using the baselines as defined above.

Measurements taken after start of administration of trial treatment will be considered either on- or off-treatment values based on the definition in [Section 6.1](#), and will be assigned to visits for statistical analysis, if applicable, as defined below.

Analysis of AE data, concomitant medication or non-drug therapies will not be based on visits. Therefore, no assignment to time windows will be necessary for such data.

For derivation of the last value on treatment, minimum value on treatment, and maximum value in the trial phase, all values from the relevant phase (whether or not collected in any time window; see [Table 6.1: 1](#) for definition of the trial phases) will be considered; these will be derived for analysis of laboratory and vital signs data. For identification of potentially clinically significant abnormal laboratory values, all values (whether or not selected in any time window) before the date of EoS Participation visit will be considered.

A graphical analysis of the ALT and total bilirubin will be performed (so called eDISH plot) based on the available data obtained during the on-treatment period.

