All other safety, efficacy and biomarker measurements will be assigned to visits based on extended time windows around the planned visit dates, defined relative to the day of first trial treatment (which is scheduled for Visit V2). These extended time windows are defined in [Table 6.7: 1](#).

Table 6.7: 1 Time windows for assignment of efficacy, safety lab, vital signs, and biomarker measurements to visits for statistical analysis

Visit number / name	Visit label	Planned day	Time window (Days)				
			Window (per CTP)	Start (per CTP)	End (per CTP)	Start (extended)	End (extended)
V1	Day 1	Day 1	n/a	1 ^A	1	1 ^A	1
V2	Week 4	Day 29	+/- 14	15	43	2	43
V3	Week 8	Day 57	+/- 14	44	71	44	71
V4	Week 12	Day 85	+/- 14	72	99	72	99
V5	Week 16	Day 113	+/- 14	100	127	100	127
V6	Week 20	Day 141	+/- 14	128	155	128	155
V7	Week 24	Day 169	+/- 14	156	183	156	183
V8	Week 28	Day 197	+/- 14	184	211	184	211
V9	Week 32	Day 225	+/- 14	212	239	212	239
V10	Week 36	Day 253	+/- 14	240	267	240	267
V11	Week 40	Day 281	+/- 14	268	295	268	295
V12	Week 44	Day 309	+/- 14	296	323	296	323
V13	Week 48	Day 337	+/- 14	324	351	324	351
V14	Week 52	Day 365	+/- 14	352	379	352	379
V15	Week 56	Day 393	+/- 14	380	407	380	407
V16	Week 60	Day 421	+/- 14	408	435	408	435
V17	Week 64	Day 449	+/- 14	436	463	436	463
V18	Week 68	Day 477	+/- 14	464	491	464	491
V19	Week 72	Day 505	+/- 14	492	519	492	519
V20	Week 76	Day 533	+/- 14	520	547	520	547
V21	Week 80	Day 561	+/- 14	548	575	548	575
V22	Week 84	Day 589	+/- 14	576	603	576	603
V23	Week 88	Day 617	+/- 14	604	631	604	631
V24	Week 92	Day 645	+/- 14	632	659	632	659
V25	Week 96	Day 673	+/- 14	660	687	660	687
V26	Week 100	Day 701	+/- 14	688	715	688	715
V27	Week 104	Day 729	+/- 14	716	743	716	743
...
V52	EoT	Day 1429	+/- 14	1415	1443	1415	1443
V53	EoS	Day 1541	+/- 14	1528	1555	1444	1555/EoT+ 16weeks

Days are counted relative to the day of first treatment, which is defined as Day 1.

^A Note that measurements made at Day 1 and assigned to the on-treatment period (because mistakenly made after start of injection of trial treatment) via assessment on date and time (i.e. safety laboratory) will not be assigned to Day 1. Such data will be listed only.

Repeated and unscheduled efficacy, safety and biomarker measurements will be handled similarly to scheduled measurements and will also be assigned to a time window depending upon the date of measurement.

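### The EoS analysis window starts at Day 1444 for every patient, so the EoS values of most early stoppers are filed under treatment weeks instead of EoS

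*SAP*

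**What the plan says.** SAP Section 5 states, for all endpoints unless specified otherwise, that the "End-of-Study visit refers to V53 (Week 220), using extended time windows as defined in" Table 6.7: 1. In that table (SAP Section 6.7) the V53 row has planned Day 1541 and an extended start of Day 1444. Its extended end is printed as "1555/EoT+ 16weeks". The EoT row (V52) runs from Day 1415 to Day 1443.

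The table footnote fixes the origin: "Days are counted relative to the day of first treatment, which is defined as Day 1". SAP Section 6.7 says that measurements "will be assigned to visits based on extended time windows around the planned visit dates, defined relative to the day of first trial treatment". It also says that values taken after the start of treatment "will be considered either on- or off-treatment values based on the definition in" SAP Section 6.1, and are then assigned to visits where applicable. Assignment by nominal visit is stated only for pre-treatment values.

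The protocol counts differently. Flow chart footnote 4 covers every dosed patient and counts from the last dose; its wording is "including those who discontinue treatment prematurely, should complete the EOT visit as soon as possible and complete the EOS visit 16 weeks after the date". Protocol Section 6.2.3 repeats it: "The EOS visit must be performed 16 weeks after the date of last drug administration". Footnote 15 adds that patients who discontinue early receive no dose at the EOT visit.

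**The concern.** The SAP window is anchored on the first dose and the protocol visit on the last dose. The two agree only for patients who complete, or nearly complete, the four years. The moving end of the EoS window suggests that a patient-specific window was intended, but a moving end cannot help when the start is fixed at Day 1444.

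Two things are at stake. First, the EoS row of a by-visit table would describe completers and near-completers and leave out most patients who stopped earlier, including those who stopped for adverse events or loss of response. Protocol Section 7.2.5 plans to compare vital signs and other safety data at the end-of-trial evaluation with the findings before treatment, and the EoS row is the natural place for that. Second, values taken 16 weeks after the last dose would appear under a treatment-week label.

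**Working it through.** **Inputs.** Dosing visits are 28 days apart, from V1 on Day 1 to V52 on Day 1429 (protocol flow chart). EoS is 16 weeks, or 112 days, after the last dose (flow chart footnote 4, protocol Section 6.2.3). The visit allowance is ±14 days (flow chart for treatment visits, Table 6.7: 1 for EoS). The windows are those of Table 6.7: 1.

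**1. The plan's own figures.** Day of visit v = 1 + 28 × (v − 1).
- V52: 1 + 28 × 51 = Day 1429.
- EoS: 1429 + 112 = Day 1541.
- Window end: 1541 + 14 = Day 1555.
- Window start, the day after the EoT window: 1429 + 14 + 1 = Day 1444.

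All match the table, so the EoS row is correct for a completer.

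**2. Who can reach the window.** The condition is last dose + 112 ≥ 1444, that is, a last dose on or after Day 1332.
- V48: Day 1317 + 112 = Day 1429, before the window.
- V49: Day 1345 + 112 = Day 1457, inside it.

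On schedule, an EoS after V49 to V52 qualifies (4 of 52 dosing visits). An EoS after V1 to V48 does not (48 of 52).

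**3. Allowing for late visits.**
- V48 dosed on time, EoS 14 days late: 1317 + 112 + 14 = Day 1443, still outside.
- V48 dosed one day late as well: 1318 + 112 + 14 = Day 1444, just inside.
- V47 with both visits 14 days late: 1289 + 14 + 112 + 14 = Day 1429, outside.

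So V48 can just qualify; V47 and earlier cannot.

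**4. The moving end.** Read as EoT + 16 weeks, the end precedes the start whenever EoT + 112 < 1444, that is, for any EoT before Day 1332. An EoT on Day 337 gives a window from Day 1444 to Day 449, which is empty. Read as Day 1555, the window is not empty, but an early EoS still falls before its start.

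**5. Where the values go.**

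| Last dose | EoS day | Window that takes it | Row |
|---|---|---|---|
| V7, Day 169 | 281 | 268–295 | Week 40 |
| V9, Day 225 | 337 | 324–351 | Week 48 |
| V13, Day 337 | 449 | 436–463 | Week 64 |
| V48, Day 1317 | 1429 | 1415–1443 | EoT |

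The Day 337 value lies exactly on the planned Week 48 day, so the closest-value rule in SAP Section 6.7 favours it.

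**6. Which rows are touched.** On schedule, last doses at V1 to V47 send EoS to V5 to V51 (47 rows), extending the printed window pattern over the rows the table leaves out. After V1, safety laboratory tests are planned at visit types D and E: Weeks 24, 48, 76, 100, 128, 152 and 180. That is 7 of the 47 rows. The other 40 have no planned laboratory test and would hold mainly samples from early EoT, EoS or unscheduled visits. Vital signs are planned at every treatment visit, so those rows stay mostly on-treatment while patients remain on drug.

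**7. How many patients.** The documents give no stopping rate. For illustration, with 40 patients and a constant annual stopping proportion r, the number still on treatment at Day 1332 is 40 × (1 − r)^(1331/365.25):

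| Assumed r | Reach Day 1332 | Do not |
|---|---|---|
| 5% | 33 | 7 |
| 10% | 27 | 13 |
| 20% | 18 | 22 |
| 30% | 11 | 29 |

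**The case against.** The strongest reply is that little depends on this row. The primary endpoint and all listed secondary endpoints are at Week 48. SAP Section 6.7 states that AE and concomitant-medication analyses are not based on visits. Last, minimum and maximum on-treatment values use every value in the phase, and potentially clinically significant laboratory abnormalities use all values before the EoS date, inside a window or not. For binary efficacy endpoints, SAP Section 6.6.2 treats data beyond the last dose + 4 weeks as missing after premature discontinuation. SAP Section 7 lists all individual values, including off-treatment ones. All of this stands and sets the limit of the point.

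A reader might infer that early stoppers' safety data are lost, or that the primary safety result is biased. The documents do not support that: the values are kept and listed, and the fault is in how they are labelled and summarised.

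A reader might also count EoS from EoT, as the table's moving end does. The protocol counts from the last dose. A patient whose last dose is V12 (Day 309) and whose EoT is Day 337 has EoS on Day 421, in the Week 60 row (Day 408 to 435), not on Day 449.

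Finally, it can be said that the moving end shows a patient-specific intent, and that the words on applicability in SAP Section 6.7 leave room to keep off-treatment values out of treatment weeks. The intent is plausible. But no rule in the visible text does this, and a programmer following the table would produce the misassignment.

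**Conclusion.** The point holds as a defect in the visit-window rule with limited reach. On schedule, the EoS row can take an EoS visit only after a last dose at V49 to V52; V48 can qualify with a late dose and a late EoS. Earlier stoppers' EoS values are assigned to scheduled-visit rows. The fixed EoT window has the same fault: an early stopper's EoT visit before Day 1415 falls in a treatment-week row.

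The certain reach is by-visit laboratory and vital-sign displays, assuming that these are measured at EoS; the EOT/EOS flow chart is not visible. If EASI and SCORAD are also measured at EoS, a value taken 16 weeks off drug could enter the continuous Week 48 summaries, because the post-discontinuation cut-off in SAP Section 6.6.2 is stated only for binary endpoints. On schedule this arises for a last dose at V9 only. The primary endpoint, AE analyses, on-treatment last, minimum and maximum values, and clinically significant laboratory abnormalities are unaffected. The number of patients concerned depends on a stopping rate that the documents do not give.

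**What to change.** In Table 6.7: 1 and the text around it:

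- Define EoT per patient as the nominal EoT visit, whatever the study day.
- Define EoS per patient as values from the day after the patient's EoT through last dose + 112 + 14 days. Count from the last dose, as the protocol does, in place of EoT + 16 weeks.
- Set last dose + 112 days as the target day for the closest-value rule. Without it, unscheduled follow-up samples and the EoS sample cannot be ranked.
- Let the V2 to V51 windows take only values dated up to the patient's EoT.
- When completing the table, check the V51 row, which is not printed. The pattern of the printed rows from V3 to V27 (planned day − 13 to + 14) would give V51 Day 1388 to 1415, and V52 starts on Day 1415. This overlap is inferred, and is at most one day.

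For a completer on schedule, target Day 1541 and end Day 1555 are unchanged. The cost is minor SAP wording and programming work, with no new data and no change to trial conduct.

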5.1 PRIMARY ENDPOINT(S)

The primary endpoint is the number (and percentage) of patients with treatment emergent adverse events (AEs) at Week 48. This will be analysed as part of the Safety analysis (see [Section 7.8](#))

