7.2.2 Primary endpoint analyses

The primary endpoint is the number of patients with treatment emergent AEs at week 48 and will be a part of the safety analysis (as described in [Section 7.2.5](#)). The primary analysis will be descriptive and will result in frequency table presenting the numbers and percentages of patients with treatment emergent AEs displayed per group as defined in [Section 7.2.1](#) and also by the following subgroups:

- Asian/Non-Asian
- Age groups: <=30 years old/>30 years old

The primary analysis will be performed on the SAF.

[figure not shown]

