7.2.5 Safety analyses

Adverse events will be coded using the Medical Dictionary for Drug Regulatory Activities (MedDRA). Standard BI summary tables and listings will be produced. All adverse events with an onset between start of treatment and end of the REP, a period of 16 weeks after the last dose of trial medication, will be assigned to the on-treatment period for evaluation.

All treated patients will be included in the safety analysis. In general, safety analyses will be descriptive in nature and will be based on BI standards. No hypothesis testing is planned.

Statistical analysis and reporting of adverse events will concentrate on treatment-emergent adverse events, i.e. all adverse events occurring between start of treatment and end of the REP. Adverse events that start before first drug intake and deteriorate under treatment will also be considered as 'treatment-emergent'.

Frequency, severity, and causal relationship of adverse events will be tabulated by system organ class and preferred term after coding according to the Medical Dictionary for Drug Regulatory Activities (MedDRA).

Laboratory data will be analysed both quantitatively as well as qualitatively. The latter will be done via comparison of laboratory data to their reference ranges. Values outside the reference range as well as values defined as clinically relevant will be summarised. Groups (defined in [Section 7.2.1](#)) will be compared descriptively with regard to distribution parameters as well as with regard to frequency and percentage of patients with abnormal values or clinically relevant abnormal values.

Vital signs, physical examinations, or other safety-relevant data observed at baseline, during the course of the trial and at the end-of-trial evaluation will be assessed with regard to possible changes compared to findings before start of treatment.

[REDACTED]

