7.4 PRIMARY ENDPOINT(S)

The primary endpoint for this trial is the number of patients with treatment emergent adverse events at Week 48.

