7.4.1 Primary analysis of the primary endpoint(s)

The analysis of the primary endpoint will be descriptive in nature and will be a part of the Safety analyses described in detail in [Section 7.8](#).

The primary analysis will be performed on the SAF.

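### Primary endpoint: the SAP sets no Week-48 limit for counting TEAEs, and its on-treatment period stops short of the Protocol's 16-week residual effect period

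*SAP*

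**What the plan says.** **Endpoint and routing.** Protocol 7.2.2 states: "The primary endpoint is the number of patients with treatment emergent AEs at week 48 and will be a part of the safety analysis". It promises a frequency table by group and subgroup on the SAF. SAP 7.4 repeats the endpoint as the "number of patients with treatment emergent adverse events at Week 48". SAP 5.1 says "This will be analysed as part of the Safety analysis", and SAP 7.4.1 says the analysis "will be a part of the Safety analyses described in detail in" Section 7.8.

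**Meaning of a week number.** SAP 5 sets a default for all endpoints: "unless explicitly specified otherwise, Week numbers refer to specific Visit numbers using extended time windows". SAP 6.7 then says: "Analysis of AE data, concomitant medication or non-drug therapies will not be based on visits". Its next sentence adds that such data need no time windows. The title of Table 6.7:1 covers efficacy, safety laboratory, vital signs and biomarkers, but not AEs.

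**TEAE period.** Protocol 7.2.5 takes AEs with onset from the start of treatment to the end of the REP, "a period of 16 weeks after the last dose of trial medication, will be assigned to the on-treatment period for evaluation". It also counts earlier AEs that worsen under treatment. SAP Table 6.1:1 starts the on-treatment period at the first injection and closes it with the EoT visit day; the day after opens an off-treatment follow-up phase. SAP 7.8.1 bases AE analysis on treatment-emergent events and places AEs starting on the day of first dosing in the on-treatment phase. It gives no end date.

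**The concern.** The trial is descriptive, so the count is the whole primary result. A programmer working from the SAP needs to know over which days a patient's AEs count. Two things are missing or inconsistent.

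First, SAP 6.7 takes AEs out of the visit-window default but does not say what Week 48 means for them instead. The section to which the endpoint is routed describes only AE analyses with no Week-48 limit.

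Second, the Protocol and the SAP use the same label, on-treatment, with different end dates. If the SAP phase were applied to AEs as written, events in the residual effect period would be dropped although the Protocol counts them as treatment-emergent. That alters the primary count for patients who stop before Week 48, and the whole-period AE tables for everyone. Early stopping is foreseeable: Protocol 1.4.2 expects that some patients may lose response, and under Protocol 4.2.2.1 use of rescue medication ends trial treatment.

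**Working it through.** The documents state no figure for this endpoint (no sample size calculation, no expected TEAE rate), so there is nothing to reproduce. The check is of dates, followed by an illustration.

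**Dates from the documents.**
- Week 48: 48 × 7 + 1 = Day 337 (V13).
- EoT for a completer: 204 × 7 + 1 = Day 1429. The last dose is given at that visit (Flow Chart footnote 15).
- REP: 16 × 7 = 112 days. For a completer it ends on Day 1429 + 112 = 1541.
- Sample size: about 40 (Protocol 7.5).

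**Where the two end dates part.** For a completer they are 112 days apart (Day 1429 against Day 1541), which matters only in the whole-period tables. An early stopper attends EOT as soon as possible (footnote 4) and EOS 16 weeks after the last dose. Assume the EoT visit falls 28 days after the last dose, and cap both periods at Day 337:

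| Last dose | SAP phase ends | Protocol period ends | Days lost before Day 337 |
|---|---|---|---|
| Day 113 | Day 141 | Day 225 | 84 |
| Day 169 | Day 197 | Day 281 | 84 |
| Day 281 | Day 309 | Day 393 | 28 |
| Day 309 | Day 337 | Day 421 | 0 |

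Under a Week-48 cut-off and this lag, patients whose last dose is on or after Day 309 are unaffected.

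**One patient.** Assume a constant TEAE onset rate, with chance of being counted = 1 − exp(−rate × days / 365.25). Take a last dose on Day 113 and rates of 0.25, 0.5, 1 and 2 per patient-year:
- Protocol period (to Day 225): 14.3%, 26.5%, 46.0%, 70.8%.
- SAP phase (to Day 141): 9.2%, 17.6%, 32.0%, 53.8%.

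**All patients.** Let p be the yearly stopping probability, h = −ln(1 − p)/365.25 the daily stopping rate, r the daily TEAE rate (yearly rate/365.25), and L the days counted after the last dose (112 for the Protocol, 28 for the SAP phase). With exponential stopping and a cap at Day 337:

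P(L) = 1 − { [h/(h + r)] × exp(−rL) × [1 − exp(−(h + r)(337 − L))] + exp(−h(337 − L)) × exp(−337r) }

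For p = 40% and 2 per year, h = 0.001399 and r = 0.005476. Then P(112) = 0.798 and P(28) = 0.744, a difference of 5.4 points (2.2 of 40). The difference P(112) − P(28), in percentage points:

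| Yearly stopping | 0.25/yr | 0.5/yr | 1/yr | 2/yr |
|---|---|---|---|---|
| 10% | 0.4 | 0.7 | 1.0 | 1.2 |
| 20% | 0.8 | 1.3 | 2.1 | 2.6 |
| 30% | 1.2 | 2.0 | 3.1 | 3.9 |
| 40% | 1.6 | 2.8 | 4.3 | 5.4 |

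The range is 0.4 to 5.4 points, or 0.1 to 2.2 of 40 patients.

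**Choice of cut-off day.** With full follow-up, moving the limit from Day 337 to Day 351 (the end of the V13 window) changes the percentage by at most about 1.5 points: at 1 per year, 60.3% against 61.7%.

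**The case against.** The strongest defence is that the SAP does not stand alone. SAP 3 says it is based on Protocol Section 7 and assumes familiarity with it. The only written definition of a TEAE is in Protocol 7.2.5, and SAP 7.8.1 uses the concept without redefining it. Table 6.1:1 defines trial phases and is not labelled a TEAE end date. Its visible uses include laboratory and vital-sign extremes, the liver plot and concomitant medication. The 7.8.1 sentence on the on-treatment phase concerns events on the day of first dosing, not the end of counting. All of this stands, and the REP may well be intended. But SAP 6.7 sends the reader to Section 7.8 for definitions used in safety analyses, and 7.8 gives no end date. It does use the name of a phase that the SAP ends earlier than the Protocol does.

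Three stronger readings are tempting and are not supported:
- *Only AEs in the V13 window (Days 324 to 351) count.* The SAP 5 default yields to explicit exceptions. SAP 6.7 makes one for AEs, and the title of Table 6.7:1 leaves AEs out.
- *The primary result will be the whole-trial count.* Both documents keep Week 48 in the endpoint, and Protocol 7.2.2 commits to a primary frequency table. The gap is that the SAP does not carry that table through with a cut-off.
- *Early stoppers lose up to 112 days.* That needs an EoT visit on the day of the last dose. It fits poorly with footnote 15, under which early stoppers receive no dose at EOT.

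Unseen text also limits the point. The list in SAP 5.4.1 breaks off, entries after 7.4.1 are blacked out in the contents, and the ADS Plan and the sponsor's AE guidance are not available. Any of these may already hold a cut-off.

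**Conclusion.** The point holds in two parts. In the visible text, the primary endpoint has no written counting interval. Cumulative counting to Week 48 is almost certainly meant but has to be inferred. In addition, the Protocol's on-treatment period for AEs and the SAP's on-treatment phase end on different dates, so the SAP applied as written can give a count other than the Protocol's.

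The effect on the primary percentage is modest: about 0.4 to 5.4 points, confined to patients who stop before Week 48. That size rests entirely on assumptions: constant onset rates of 0.25 to 2 per patient-year, 10 to 40% stopping per year, and a 28-day lag to the EoT visit. No test, power or conduct of the trial is affected. It should be settled before the final analysis because it concerns the sole primary endpoint.

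**What to change.** In SAP 5.1 and 7.4.1, define the endpoint as the number (%) of SAF patients with at least one TEAE, including pre-existing AEs that worsen (Protocol 7.2.5), from first dose to the earlier of Day 337 and the end of the TEAE period. Produce it as its own table, with the groups and subgroups of Protocol 7.2.2, apart from the whole-period AE tables.

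In SAP 7.8.1, state for AE analyses the Protocol 7.2.5 period (first dose to last dose + 16 weeks). Say that it is separate from the Table 6.1:1 phases used for laboratory and vital-sign data. If a departure from the Protocol is intended, state it and justify it.

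If the ADS Plan, the sponsor's AE guidance or redacted text already fixes a cut-off, state that in SAP 5.1.

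Cost: a few SAP sentences, one extra table and a little programming, using onset, dosing and visit dates already collected.
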